3.5. DETERMINATION OF SAMPLE SIZE

A sample size of 186 subjects (93 per treatment group) provides 90% power, with a two-sided significance level of 5%, of obtaining a statistically significant difference between two treatment groups for the distance walked during the 12MWT. This assumes a treatment effect (difference versus placebo in mean change from baseline) size of 60 meters. The standard deviation for the changes from baseline observed in Study [REN001-101](#) was approximately 100 meters. A higher standard deviation, 125 meters, was assumed for this study due to the longer assessment period (24 weeks instead of 12 weeks) and the larger number of sites included in this study. Allowing for a reduction in power due to subject withdrawals, a total of approximately 200 subjects was determined as the appropriate sample size.

The sample size for the DXA sub-study is not based on statistical justification. This sub-study is exploratory in nature and limited to REN001-201 sites that have approval to conduct this sub-study.

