- Menopausal status: males, pre-menopausal females or post-menopausal females. Post-menopausal females have a screening FSH value ≥ 23.0 IU/L and with either a date of last menstrual period > 1 year ago from date of first dose or a confirmed clinical history of sterility. Female subjects whose last menstrual period was > 1 year ago but do not have a screening FSH value will also be assumed to be post-menopausal. Female subjects who have a clinical history of sterility but do not have a screening FSH value cannot be classified. This subgroup will only be used for DXA and laboratory bone marker analyses.

The number of subjects in each subgroup has been assessed using blinded baseline data. The review did not identify any subgroup categories to combine, however it has been agreed that only subgroup categories with 5 or more subjects will be summarized and only subgroup categories with 30 or more subjects will be analysed. In addition to this the following decisions were made:

- Race = other will not be summarized
- Country and 30STS subgroups will only be summarized
- All mutational genotype subgroup categories and baseline 12MWD categories will be summarized and analysed
- Syndromatic phenotype subgroup category MERF will be analysed as well as summarized.

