10.1.2. Primary Analysis

Intercurrent events and missing data will be handled using the methodology described in [Section 8.3.1](#). For the primary endpoint the missing values will be imputed using the technique of multiple imputations; this includes incomplete tests considered unrelated to their PMM, which will be set to missing prior to imputation. The multiple imputation step will be performed prior to any imputations for intercurrent events.

Changes from baseline will be analysed using a MMRM. The model will include fixed terms for treatment, visit and the treatment-by-visit interaction. The model will also include the stratification mutation factor and continuous baseline distance walked during the 12MWT as covariates. An unstructured covariance matrix will be used for the repeated visits within a subject and the model will allow the covariance matrix to differ between treatment groups. If this analysis fails to converge, then an analysis of covariance (ANCOVA) will be used which will analyse the change from baseline at Week 24 and at Week 12 separately. The ANCOVA model will include a fixed term for treatment and the mutation stratification factor and continuous baseline distance walked during the 12MWT as covariates. The Kenward-Rogers approximation will be used to estimate the denominator degrees of freedom ([Kenward 1997](#)). The treatment comparison (mavodelpar 100mg - placebo) for the change from baseline at both Week 12 and Week 24 will be estimated. The estimates, standard errors, 95% confidence intervals and associated p-values will be presented for each of the multiple imputation analyses as well as the pooled values.

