10.1.6. Subgroup Analyses

The impact of all subgroups (specified in [Section 8.5](#)) on the primary endpoint will also be investigated descriptively. Summaries will be presented by subgroup and the imputed

datasets generated for the primary analysis will be analysed by subgroup using the primary analysis model. A forest plot of the estimate of the treatment difference and associated 95% confidence interval for each subgroup will be presented for Weeks 12 and 24.

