- Observed values for endpoint at each visit are contained in the variables - `scrn`=screening, `bl`=baseline, `w12`=week 12, `w24`=week 24
- If a subject has a missing baseline (either not collected or out of window) then the screening value will be used as baseline. However, for the multiple imputation model the time the data was collected will be preserved so the `scrn` variable will be the screening value and the `bl` variable will be missing and imputed. The imputed baseline values will only be used to facilitate the imputation of later visits but will not be used in the analyses.
- mutation is 2 levels e.g. 1=m.3243>G; 2=Other
- treatment is 2 levels e.g. 1=REN001; 2=Placebo

4: Combining multiple imputation analyses using MIANALYZE.

```
ODS OUTPUT PARAMETERESTIMATES=<outestdataset>;  
proc mianalyze data=<diffsdataset>;  
by visit;  
modeleffects estimate;  
stderr stderr;  
run;
```

Assumptions:

- Convert the resulting MI dataset to a vertical structure and analyse using MMRM (SAS code point 1) by imputation. Output the dataset of estimates (ODS OUTPUT DIFFS=<diffsdataset>;) keeping the visit comparisons of interest. Use this dataset in the MIANALYZE procedure.

Secondary Endpoint Analyses

5: PROMIS T-score - Repeated measures mixed model analysis (MMRM).

```
proc mixed data=<dataset>;  
  class treatment(ref='Placebo') visit subject mutation(ref='Other');  
  model chg=mutation base12mwd baseline treatment visit treatment*visit /  
        ddfm=kr solution;  
  repeated visit / subject=subject type=un group=treatment;  
  lsmeans treatment*visit / cl diff;  
  estimate 'REN001 - Placebo: W4' treatment 1 -1 treatment*visit 1 0 0 0 -  
1 0 0 0/cl;  
  estimate 'REN001 - Placebo: W12' treatment 1 -1 treatment*visit 0 1 0 0  
0 -1 0 0/cl;  
  estimate 'REN001 - Placebo: W18' treatment 1 -1 treatment*visit 0 0 1 0  
0 0 -1 0/cl;  
  estimate 'REN001 - Placebo: W24' treatment 1 -1 treatment*visit 0 0 0 1  
0 0 0 -1/cl;  
run;
```

Assumptions:

- treatment is 2 levels e.g. 1=REN001; 2=Placebo
- visit is 4 levels e.g. 1=Week 4; 2=Week 12; 3=Week 18; 4=Week 24
- mutation is 2 levels e.g. 1=m.3243>G; 2=Other
- chg is change from baseline; baseline is baseline score
- base12mwd is the Baseline 12MWD
- An unstructured covariance matrix is specified using type=un. If this analysis fails to converge, then an ANCOVA approach will be used instead.

Exploratory Endpoint Analyses

6: PGIC - ANCOVA.

```
proc mixed data=<dataset>;  

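### The MIANALYZE code gives the pooled primary and PROMIS tests Rubin's large-sample degrees of freedom instead of ones consistent with Kenward-Roger; the effect is small and cheap to remove

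*SAP*

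**What the plan says.** On the primary MMRM, SAP 10.1.2 states: "The Kenward-Rogers approximation will be used to estimate the denominator degrees of freedom". SAP 10.2.1 says the same for the PROMIS T-score. Both sections report confidence intervals and p-values for each imputation and for the pooled result. The MIXED code in Appendix 1 (items 1 and 5) requests `ddfm=kr`.

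Pooling is described in SAP 8.3.1, which cites Rubin's 1987 rules, plans 25 imputations, and names no small-sample degrees of freedom. In Appendix 1, item 4, the MIANALYZE call runs by visit and contains "modeleffects estimate" and a STDERR statement. No `EDF=` value is given.

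Subgroups use the same machinery. SAP 10.1.6 says that the imputed "datasets generated for the primary analysis will be analysed by subgroup using the primary analysis model", with 95% intervals in forest plots. SAP 8.5 sets a general minimum of 30 subjects for analysis, but adds: "All mutational genotype subgroup categories and baseline 12MWD categories will be summarized and analysed". The MERF phenotype category is also analysed regardless of that minimum. SAP 10.1.5 notes that few subjects have a baseline 12MWD of 500 m or less.

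**The concern.** Without `EDF=`, MIANALYZE takes the complete-data degrees of freedom as infinite. The pooled degrees of freedom then depend only on the number of imputations and the share of variance due to missing data, not on sample size. The small-sample degrees of freedom computed in each MIXED run are left behind at the pooling step, and the pooled result is the one tested in the fixed sequence (SAP 8.2).

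The direction is known: too many degrees of freedom give a critical value that is too small, so p-values are slightly low and intervals slightly narrow. At stake are the exact 5% level of the two confirmatory tests and the width of the subgroup intervals.

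**Working it through.** **The plan's own figure.** The SAP assumes a "treatment effect (difference versus placebo in mean change from baseline) size of 60 meters" and says "A higher standard deviation, 125 meters, was assumed for this study". With 93 per group and two-sided 5%, the noncentral t gives power 0.9025 (0.899 at 92 per group), so the stated 186 for 90% power reproduces. The plan then says "a total of approximately 200 subjects was determined as the appropriate sample size", an allowance of (200 − 186)/200 = 7% for withdrawals. The documents state no pooled degrees of freedom.

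**Inputs**
- m = 25 imputations (SAP 8.3.1).
- Relative increase in variance from missing data, r = (1 + 1/m)B/W: assumed 0.02 to 0.10. Fraction λ = r/(1 + r) = 0.0196 to 0.0909.
- Complete-data degrees of freedom ν: assumed about 195 at 200 patients and about 25 at 30 patients. The actual Kenward-Roger values will differ by visit and imputation.

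**Formulas**
- As coded (Rubin 1987): df = (m − 1)(1 + 1/r)².
- Barnard-Rubin: ν_obs = ν(1 − λ)(ν + 1)/(ν + 3), then df* = 1/(1/df + 1/ν_obs).
- Actual level of the coded test, taking df* as correct: 2·P(t_df* > t_0.975,df).

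**Coded df**
- r = 0.02: 24 × 51² = 62,424, critical value 1.960.
- r = 0.10: 24 × 11² = 2,904, critical value 1.961.

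**Results**

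| Complete-data df | r | ν_obs | df* | Critical value, coded | Critical value, Barnard-Rubin | Interval too narrow by | Level at nominal 5% |
|---|---|---|---|---|---|---|---|
| 195 | 0.02 | 189.2 | 188.7 | 1.960 | 1.973 | 0.6% | 5.15% |
| 195 | 0.10 | 175.5 | 165.5 | 1.961 | 1.974 | 0.7% | 5.16% |
| 25 | 0.02 | 22.8 | 22.7 | 1.960 | 2.070 | 5.3% | see below |
| 25 | 0.10 | 21.1 | 21.0 | 1.961 | 2.080 | 5.7% | see below |

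At 200 patients (ν = 196), raising λ to 0.30 moves the figures only to 1.969 against 1.987, 0.9% too narrow and 5.20%.

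**Why the subgroup rows stop at width.** The formula level at 30 patients would be about 6.2-6.3%, but it holds only if Rubin's variance is right within the subgroup. SAP 8.3.1 imputes within each whole treatment arm, and 10.1.6 then analyses subsets of those data sets. The imputations use more information than the subgroup model does, so Rubin's variance tends to be too large within the subgroup.

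A simulation checked this: 200 patients, imputation by arm, 25 imputations, ANCOVA, no treatment effect and no subgroup heterogeneity, 20,000-25,000 runs per setting. Rejection rates were:

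| Patients analysed | Missing at Week 24 | No EDF | With EDF |
|---|---|---|---|
| 200 | 10% | 0.051 | 0.049 |
| 30 | 3% | 0.057 | 0.046 |
| 30 | 10% | 0.046 | 0.036 |

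A further set of runs with 2-10% missing gave 0.038-0.054 without EDF at 30 patients and 0.030-0.042 with it. So the coded subgroup interval can lie on either side of nominal coverage, and the EDF version was conservative at 30 patients in every setting run.

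**The case against.** The best defence is that the code follows the pooling rule as written. SAP 8.3.1 and protocol 8.5.1 cite Rubin's 1987 rules only; the Kenward-Roger sentence can be read as describing each MMRM fit, where `ddfm=kr` is coded; and SAP section 10 calls the appendix sample code. On that reading Barnard-Rubin is a refinement. This stands in part: the code does not contradict 8.3.1. But 10.1.2 and 10.2.1 attach Kenward-Roger to results that include the pooled values, and no sentence says which degrees of freedom govern the pooled test.

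The second defence is size. At 200 patients the two rules are almost indistinguishable. This stands in full.

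Two stronger readings are tempting. A reader might infer that the Kenward-Roger adjustment is lost altogether at pooling. It is not: the adjusted standard error enters through the STDERR statement, and per-imputation results keep full Kenward-Roger inference. A reader might also infer that small-subgroup intervals clearly under-cover. The documents do not support that. Imputation from the whole arm can offset the effect, the sizes of the exempt subgroups are not stated, and SAP 8.5 and 10.1.6 make subgroups descriptive, with no place in the fixed sequence.

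**Conclusion.** The gap is real and minor. The pooled 12MWD and PROMIS tests are slightly liberal. A p-value of 0.05 under Barnard-Rubin would be reported as about 0.048, so a conclusion could change only in that narrow band. For subgroups near 30 patients, what is shown is narrower intervals relative to Kenward-Roger-consistent pooling, not coverage below 95%.

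The direction for the degrees of freedom follows from the code. The size rests on the assumed r and complete-data degrees of freedom, neither of which the documents give. The separate covariance matrix per arm in the model could lower the Kenward-Roger values where arms are unequal. The PROMIS figures carry over only if its complete-data degrees of freedom are similar.

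**What to change.** - For the pooled primary and PROMIS analyses and their imputation-based sensitivity analyses, run MIANALYZE separately for each visit with `EDF=` set to the Kenward-Roger degrees of freedom for that contrast. These are already in the DIFFS data set that item 4 uses; the minimum over the 25 imputations is a simple, prespecifiable choice.
- State in SAP 8.3.1 that pooled inference uses Barnard-Rubin degrees of freedom, and how the complete-data value is chosen.
- Apply the same rule to the subgroup intervals for consistency, noting that they become wider and may be conservative.

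`EDF=` takes one value per call, so the present by-visit call must be split (two visits for 12MWD, four for PROMIS, and per subgroup). The cost is a short macro and one sentence in the SAP, plus confirmatory intervals wider by under 1% in the cases shown. No data collection or sample size change is needed.
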